2.7.2. Treatment Exposure and Compliance

Compliance by treatment and by visit

Records of changes in medication are to be kept during the study. Throughout the study, subjects will be instructed about the importance of medication adherence and asked to take any required study-defined antihypertensive treatment at approximately 08:00 am daily except on the morning of each office visit when they will be asked to bring their protocol-defined medication with them to the visit.

Adherence to drug therapy will be captured by interviewing patients, checking the patient's BP diary and by urinary toxicological analysis at baseline, 6 month, and 12 month visit.

2.7.3. Efficacy measures

2.7.3.1. Primary and secondary efficacy variables

Office Blood Pressure Measurements

The measurement of office BP was done according the following guidelines based on the 2018 ESH/ESC Guidelines for the management of arterial hypertension. [5]

24-h ambulatory BP Measurements

The measurement of 24-h ambulatory BP will occur at -4, -1, 12, 26, and 52 weeks FU visits with the ambulatory BP system (Mobilograph®, I.E.M. Stolberg, Germany; 90207 or 90217A, Spacelabs Healthcare, Meerbusch, Germany). Only ambulatory BP recordings with a minimum of 28 measurements during the 24 hour period will be considered valid. The measurement of ambulatory BP was done according the following guidelines based on the 2018 ESH/ESC Guidelines for the management of arterial hypertension. [5]

Home BP Measurements

Home BP measurements are introduced to increase safety for the patients, not for efficacy. After education on the use of the Home BP system, all subjects will be provided with a Home BP monitor (apnorm® Professional Touch, microlife, Widnau, Switzerland).

eGFR Calculation

eGFR calculations for inclusion will be standardized using the currently used estimation formulas (MDRD, CKD-EPI).

Laboratory Assessments

All subjects will have blood collected at every visit. In addition, all subjects will have urine samples collected at -4, -1, 12, 26, and 52 week follow-up visits for urine analysis. Females of child bearing potential will have a urine or blood plasma pregnancy test up to 7 days prior to the procedure.

Laboratory Data	
Blood Chemistry	urea, creatinine, eGFR, cystatin C, uric acid, sodium, potassium, calcium, γ -GT, GOT, GPT, alkaline phosphatase, total cholesterol, LDL-cholesterol, HDL-cholesterol, triglycerides, total serum protein Fasting blood glucose, HbA1c
Hematology	hemoglobin, hematocrit, erythrocyte count, platelet count, white blood count
Urin analysis	Spot urine (urinary creatinine, protein, albumin, sodium and potassium), Urine pregnancy testing (applicable females only)

HP LC-MS/MS of Antihypertensive Adherence

HP LC-MS/MS is a recognized method with good to excellent sensitivity and specificity to detect many pharmacological agents in urine. Urine collected at -1 and 26 and 52 weeks FUs will be sent for analysis.

2.8. Safety and Tolerability Measures

Term	Definition
Adverse Event (AE) Ref: ISO 14155-2011	Any untoward medical occurrence, unintended disease or injury, or untoward clinical signs (including abnormal laboratory findings) in subjects, users or other persons, whether or not related to the investigational medical device. NOTE 1: This definition includes events related to the investigational medical device or the comparator. NOTE 2: This definition includes events related to the procedures involved NOTE 3: For users or other persons, this definition is restricted to events related to the investigational medical device.
Adverse Device Effect (ADE) Ref: ISO 14155-2011	AE related to the use of an investigational medical device NOTE 1: This definition includes adverse events resulting from insufficient or inadequate instructions for use, deployment, implantation, installation, or operation, or any malfunction of the investigational medical device. NOTE 2: This definition includes any event resulting from use error or from intentional misuse of the investigational medical device.
Serious Adverse Event (SAE) Ref: Ordinance on Medical Devices Vigilance (MPSV)	Adverse event that directly or indirectly have led, might have led, or might lead to death or to a serious deterioration in the health of a subject, user, or other person, whether or not related to the investigational medical device,
Serious Adverse Device Effect (SADE) Ref: ISO 14155-2011	Adverse device effect that has resulted in any of the consequences characteristic of a SAE.
Unanticipated Serious Adverse Device Effect (USADE) Ref: ISO 14155-2011	Serious adverse device effect which by its nature, incidence, severity, or outcome has not been identified in the current version of the risk analysis report. NOTE 1: Anticipated serious adverse device effect (ASADE) is an effect which by its nature, incidence, severity or outcome has been identified in the risk analysis report.
Device Deficiency Ref: ISO 14155-2011	Inadequacy of a medical device with respect to its identity, quality, durability, reliability, safety or performance. NOTE: Device deficiencies include malfunctions, use errors, and inadequate labelling.

Definitions of Adverse Events and Device Deficiency

Assessment of Severity

The clinical severity of an AE will be classified as:

Mild: asymptomatic or mild symptoms; clinical or diagnostic observations only; intervention not indicated.

Moderate: minimal, local or non-invasive intervention indicated; limiting age-appropriate instrumental activities of daily living.

Severe: severe or medically significant but not immediately life-threatening; hospitalization or prolongation of hospitalization indicated; disabling; limiting self care activities of daily living.

Life-threatening: Life-threatening consequences; urgent intervention indicated

Fatal: Death related to AE

The definitions above are difficult to apply for some data (e.g. clinically relevant laboratory values that are documented and evaluated on the CRF AE report form). In such situations, the investigator made a judgment based on personal experience.

Assessment of Seriousness

The seriousness were assessed by the investigator and the Sponsor.

Assessment of Causality

The relationship between the use of the investigational medical device (including the medical-surgical procedure) and the occurrence of each adverse event were assessed and classified according to five different levels of causality:

Not related: relationship to the device or procedures can be excluded when:

- the event is not a known side effect of the product category the device belongs to or of similar devices and procedures;
- the event has no temporal relationship with the use of the medical device or the procedures;
- the event does not follow a known response pattern to the medical device (if the response pattern is previously known) and is biologically implausible;
- the discontinuation of medical device application or the reduction of the level of activation/exposure - when clinically feasible - and reintroduction of its use (or increase of the level of activation/exposure), do not impact on the event;
- the event involves a body-site or an organ not expected to be affected by the device or procedure;

- the event can be attributed to another cause (e.g. an underlying or concurrent illness/ clinical condition, an effect of another device, drug, treatment or other risk factors);
- the event does not depend on a false result given by the medical device used for diagnosis, when applicable;
- harms to the subject are not clearly due to use error;
- In order to establish the non-relatedness, not all the criteria listed above might be met at the same time, depending on the type of device/procedures and the event.

Unlikely: the relationship with the use of the device seems not relevant and/or the event can be reasonably explained by another cause, but additional information may be obtained

Possibly related: the relationship with the use of the medical device is weak but cannot be ruled out completely. Alternative causes are also possible (e.g. an underlying or concurrent illness/clinical condition or/and an effect of another device, drug or treatment). Cases where relatedness cannot be assessed or no information has been obtained should also be classified as possible.

Probably related: the relationship with the use of the investigational device seems relevant and/or the event cannot reasonably be explained by another cause, but additional information may be obtained.

Causal relationship: the adverse event is associated with the investigational device or with procedures beyond reasonable doubt when:

- the event is a known side effect of the product category the device belongs to or of similar devices and procedures;
- the event has a temporal relationship with device use/application or procedures;
- the event involves a body-site or organ that the medical device or procedures are applied to or the medical device or procedures have an effect on;
- the event follows a known response pattern to the medical device (if the response pattern is previously known);

- the discontinuation of medical device application (or reduction of the level of activation/exposure) and reintroduction of its use (or increase of the level of activation/exposure), impact on the event (when clinically feasible);
- other possible causes (e.g. an underlying or concurrent illness/clinical condition or/and an effect of another device, drug or treatment) have been adequately ruled out;
- harm to the subject is due to error in use;
- the event depends on a false result given by the medical device used for diagnosis , when applicable;
- In order to establish the relatedness, not all the criteria listed above might be met at the same time, depending on the type of device/procedures and the event.

Assessment of Expectedness

The expectedness was assessed by the Sponsor for SADEs only:

An Unanticipated Serious Adverse Device Defect is a Serious Adverse Device Effect which by its nature, incidence, severity, or outcome has not been identified in the current version of the risk analysis report.

Categories of Patient Outcome

The reportable outcomes and/or sequelae of an AE are as follows:

- Resolved
- Resolved with sequelae
- Ongoing
- Death

Recording and Reporting of Adverse Events

The period of observation for AEs extends from Study Screening/Baseline Eligibility Visit 1 (Week -4) until Visit 10 (Week +52). New AEs reported to the investigator during the observational period, after the study procedure must be documented, treated, and followed up like all other AEs.

AEs will not be followed up after the final investigation visit which is scheduled 12 months after the treatment with the investigational medical device.

Underlying diseases/pre-existing conditions that do not worsen during the course of the investigation are not reportable as AEs. To determine whether a condition has worsened, it is compared to the condition of the subject at baseline.

Elective treatments planned before screening and which are documented in the subject's source data are usually not regarded as AEs.

Data pertaining to AEs will be collected during each investigation visit based through the investigators inquiry or discovered in the course of examinations done during the visit. The investigators will assess and record any AE in detail in the subject file and on the CRF AE report form.

The following information were recorded:

- AE diagnosis or main symptom.
- Date of event onset.
- Severity
- Investigational medical device (blinded)
- Causal relationship (causal related, probably related, possibly related, unlikely related, not related).
- Serious (yes or no).
- Patient outcome
- Action taken /treatment.
- AE falling under the definition of an AESI (yes or no)
- AE leading to discontinuation of the investigation (yes or no)
- AE due to a device deficiency (yes/no)
- Date of event resolution

After completion of all scheduled visit assessments the investigator must document any AEs arising from these assessments. In case of an SAE, the investigator must also complete an SAE report form.

Recording and Reporting of Serious Adverse Events

All SAEs that occur during the investigation period, whether considered to be related to the investigational medical device/procedures or not, were reported by the investigator to the Sponsor within 24 hours of knowledge.

SAE report forms are provided in the ISF. Completed reports were signed by an investigator and transferred by fax to:

Medical Device Vigilance Office
Center for Clinical Studies (CCS Erlangen)
Universitätsklinikum Erlangen
[name]

[name]
[contact]
email: [contact]

Although all information required for completion of an SAE report form may not be available within the specified time period, an initial report were submitted if the following minimal information is available:

- An identifiable subject (subject ID).
- An identifiable reporting source (investigator/investigation site identification).
- An event or outcome that can be identified as serious.

The investigator must supply further supporting information within 3 days of knowledge of the SAE, and a detailed SAE description is an integral part of this supporting information. Follow-up reports should be sent without delay to the addressee mentioned above as an SAE report form (marked as a “follow-up” report) and accompanied by appropriate supporting documentation (e.g., hospital reports). The SAE has to be followed up until a final outcome and date are available.

SAEs occurring after the end of the observational period need only be reported if the investigator considers the event to be related to the investigational medical device or procedures. These reports generally will not be entered into the study database.

- If a causal relationship between the SAE and the investigational medical device, a comparator device, diagnostic or therapeutic procedures performed as part of the clinical trial or other conditions of the trial conduct cannot be excluded:

SAE report immediately, as a single report on the German SAE report form to [contact]

- If A causal relationship between the SAE and the investigational medical device, a comparator device, diagnostic or therapeutic procedures performed as part of the clinical trial or other conditions of the trial conduct can be excluded:

SAE reports quarterly, as a summary table on the MEDDEV 2.7/3 SAE report table to [contact]

- In addition all SAE reports quarterly together with a SAE summary evaluation

Recording and Reporting of Device deficiencies

Device deficiencies are defined as inadequacy of a medical device with respect to its identity, quality, durability, reliability, safety and performance. The investigator will record and assess any device deficiency in detail on the CRF Device Deficiency Form.

Recording and Reporting of Pregnancies

Each pregnancy that becomes known during the investigation in a female participant must be reported by the investigator to the addressee mentioned above (see 13.3.2) within 24 hours of learning of its occurrence and followed up until 8 post partum. Pregnancies and pregnancy follow-up should be reported on a Pregnancy Monitoring Form. Pregnancy follow-up should describe the outcome of the pregnancy, including any voluntary or spontaneous discontinuation; details of the birth; the presence or absence of any congenital abnormalities, birth defects, maternal or newborn complications, and their relation to the investigational medical device/procedures. Each pregnancy has to be reported as a non-serious AE (device exposure before or during pregnancy) as well.

2.9. General Analysis

2.9.1. General Methodology

Descriptive statistics will be displayed for all documented and derived variables. For continuous variables, number of observations, number of missing values, mean, standard deviation, minimum, median and maximum will be calculated. For categorical variables, number of patients, absolute and relative frequencies will be calculated.

In this parallel, controlled study, data analysis will be performed using unadjusted analysis, i.e. simple paired and unpaired t-test under the assumption of a normal distribution for the difference of interest.

2.9.2. General Information about the Conduct of the Study

General information about the conduct of the trial will be displayed as follows:

The date of first subject in, last subject out and trial duration (duration in days between the first subject in and the last subject out) will be described.

The patient disposition (accounting of patients) will be presented by displaying the number of patients belonging to the different analysis populations.

The number of discontinued subjects and the reasons for discontinuation, on the screened population will be described.

2.9.3. Analysis of Demographic and other Baseline Characteristics

Demographic and patient characteristics will be summarized in tables and listings for the SAF, ITT, modified ITT, PPP, modified PPP, Bavarian population, separated by treatment groups and for the total population.

The demographic characteristics are: age and gender etc.

Summary of medical history and prior or concomitant medication will be presented.

The summary of medical history and current medical conditions including all previous and current medical conditions will be presented by preferred term and by body system of the system.

Baseline values of the efficacy measures will be presented in the efficacy section.

Baseline laboratory values will be presented.

Data from patients who were enrolled into the study, but not treated renal denervation or sham, will be presented in listings. No further analyses will be done with these patients' data.

2.9.4. Analysis of Efficacy

The primary analysis will be conducted on the ITT population.

2.9.4.1. Primary efficacy variable

Primary variable is the change in systolic 24-h ambulatory BP at 6 months post-procedure compared between the 2 groups.

Hence, (e.g.) the following null hypotheses H_0 , will be tested against their alternative hypotheses H_1 using unpaired t-test:

H_0 : There is no significant difference in systolic 24-h ambulatory BP at 6 months post-renal denervation compared between the 2 groups. (RDN group vs. sham group)

H_1 : There is a significant difference in systolic 24-h ambulatory BP at 6 months post-renal denervation compared between the 2 groups (RDN group vs. sham group).

The overall significance level of the trial is defined as $\alpha = 0.05$ (two-sided).

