1.1.1. Primary objective

The primary efficacy parameter is:

- Change in systolic 24-h ambulatory BP at 6 months post-RDN-procedure from pre-procedure (including 1. Pre-treatment value (**P**) = average of the pre-procedure visit (week -1) value and screening visit (week -4) value, 2. Baseline value (**B**) = pre-procedure visit (week -1) value only) compared *between the 2 groups* (RDN-Treatment group vs. Sham group).

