- Change in number of antihypertensive drugs at 3, 6 and 12 months post-procedure from pre-procedure (pre-procedure visit (week -1)) compared between the 2 groups.
- Change in drug burden index at 3, 6 and 12 months post-procedure compared from pre-procedure (pre-procedure visit (week -1)) between the 2 groups (RDN-Treatment group vs. Sham group).
- Change in antihypertensive load index at 3, 6 and 12 months post-procedure from pre-procedure (pre-procedure visit (week -1)) compared between the 2 groups (RDN-Treatment group vs. Sham group).
- Percentage of subjects requiring initiation of additional antihypertensive drug therapy between 3 and 6 months post-procedure compared between the 2 groups (RDN-Treatment group vs. Sham group).
- Change in following body fluid composition parameters measured by the Body Composition Monitor (BCM), Fresenius Medical Care at 3, 6 and 12 months post-procedure from pre-procedure (pre-procedure visit (week -1)) compared between the 2 groups (RDN-Treatment group vs. Sham group)
 - o Weight, height, BMI, Overhydration (OH), OH % of extra cellular water
- Change in following parameters at all ambulatory BP measurements (24 hours ambulatory values, ambulatory values- day time and ambulatory values- night time) derived from Mobilograph® examination at 3, 6 and 12 months post-procedure from (pre-procedure visit (week -1)) compared between the 2 groups (RDN-Treatment group vs. Sham group).
 - o Pulse pressure, central systolic pressure (zSys), central diastolic pressure (zDia), augmentation index at 75 beats per minute (AIx at 75 bpm), heart minute volume (HMV), peripheral resistance, reflexion coefficient, pulse wave velocity (PWV)

All the analyses with respect to the 24 hour ambulatory parameters or office blood pressure parameters described under 1.1.1, 1.1.2 and 1.1.3 will be performed by comparing the treatment values at 3, 6, and 12 months from the pre-procedure value (1. Pre-treatment value (**P**) = average of the pre-procedure visit (week -1) value and screening visit (week - 4) value, 2. Baseline value (**B**) = pre-procedure visit (week -1) value only) in the RDN group and the sham group, separately (paired analyses) and compared *between the 2 groups*.

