2.4. Analyses

Statistical analyses will be based on the basis of international guidelines (CPMP/ICH/363/96:E9). Due to the early stop of the study, only an exploratory and descriptive analysis takes place. Statistical methods used to compare groups for primary and secondary outcomes:

Efficacy: Change of systolic 24-h ambulatory BP at 6 months post-procedure (primary efficacy endpoint) compared between the RDN and sham group will be analyzed in a linear mixed model including the covariates that were significantly different between the groups at baseline. All secondary (see 1.1.2) and observational endpoints (1.1.3 and 1.1.4) are analyzed also via a modelling approach adjusting for potential imbalances in baseline characteristics. The type I error for the analysis of the primary endpoint is set at 5% (two-sided), all analyses of secondary endpoints have an exploratory character avoiding multiplicity issues in this trial.

In addition, a win ratio analysis will be conducted, with the criteria 24h ambulatory systolic BP change > 5 mmHg, office systolic BP change > 10 mmHg, and decrease of medication as defined by following 3 parameters (number of antihypertensive drugs, drug burden index and antihypertensive load index).

Analysis will be performed for the following populations:

1. Primary analysis is based on *the intention-to-treat* (ITT) population consisting of all randomized study subjects that are all either RDN treated or sham treated.
2. A secondary analysis will be done with a *modified ITT* population (mITT) in which participants with adherence violations will be excluded (sensitivity analyses).
3. A secondary analysis will be done with the *per protocol population* (PPP) in which study subjects with predefined protocol deviations (defined prior to unblinding of the data) are excluded.
4. A secondary analysis will be done with the modified *per protocol population* (mPPP) in which study subjects of the PPP with adherence violation are excluded.
5. A secondary analysis will be done with the safety population (SAF) in which all study subjects signing informed consent are included.

6. A secondary analysis will be done with those patients that are investigated by the Erlanger and Nürnberger center (CRC staff), with a total of N=20 randomized patients (Bavarian cohort)

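### The SAP names two conflicting primary methods and two unranked baselines, and attaches a 5% level to an analysis it also calls exploratory only

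*SAP*

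**What the plan says.** **Method.** SAP 2.4 states that the 6-month change in 24-h systolic ambulatory BP "will be analyzed in a linear mixed model including the covariates that were significantly different between the groups at baseline". SAP 2.9.4.1, the section devoted to the primary variable, states that the hypotheses "will be tested against their alternative hypotheses H_1 using unpaired t-test", and opens that sentence with an e.g. in brackets. SAP 2.9.1 says "data analysis will be performed using unadjusted analysis, i.e. simple paired and unpaired t-test".

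**Baseline.** SAP 1.1.1 (repeated in 2.1) defines the endpoint as "Change in systolic 24-h ambulatory BP at 6 months post-RDN-procedure from pre-procedure (including 1. Pre-treatment value" P, and then also from B. P is the mean of weeks -4 and -1; B is week -1 alone. The last paragraph of 1.1.3 says all ambulatory and office BP analyses "will be performed by comparing the treatment values at 3, 6, and 12 months from the pre-procedure value (1. Pre-treatment value" P, and again B as well. Section 2.9.4.1 does not say which baseline its test uses.

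**Hypotheses.** Section 2.9.4.1 calls the primary variable a change, but words H0 and H1 on BP at 6 months.

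**Status.** Section 2.4 says: "Due to the early stop of the study, only an exploratory and descriptive analysis takes place". The same section sets a two-sided 5% type I error for the primary endpoint and describes only the secondary endpoints as exploratory in order to avoid multiplicity. Section 2.9.4.1 adds: "The overall significance level of the trial is defined as" 0.05, two-sided.

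**The concern.** An adjusted model and an unadjusted t-test cannot both be the primary analysis, and the SAP gives neither precedence. Crossed with two unranked baselines, this leaves four candidate primary results. The SAP does not say whether one significant result is enough, whether all are needed, or whether none carries a confirmatory claim.

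Two analysts could follow this SAP faithfully and report different primary p-values. The choice could also be made after the treatment codes are known. A 5% error level has meaning only when it belongs to one identified test or to a stated rule for combining several. Here it belongs to neither.

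**Working it through.** **1. The texts side by side**

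| Element | One statement | Other statement | Ranking given? |
|---|---|---|---|
| Method | 2.4: linear mixed model, adjusted | 2.9.1 and 2.9.4.1: unadjusted, unpaired t-test | No |
| Baseline | 1.1.1, 1.1.3, 2.1: P | same sections: B | No |
| Quantity tested | 2.9.4.1: change is the primary variable | 2.9.4.1: H0/H1 on BP at 6 months | No |
| Status | 2.4: exploratory and descriptive only | 2.4 and 2.9.4.1: 5% two-sided | No |
| Primary set (ITT) | 2.3: randomised with a post-procedure efficacy measurement | 2.4: all randomised and treated; no measurement needed | No |

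Two methods times two baselines give four versions, before counting the two readings of ITT.

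**2. The SAP's own figure**

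The 5% is a chosen level, so there is nothing to derive. It holds for one pre-specified t-test. For k independent tests the chance of at least one p<0.05 under no effect is 1 − 0.95^k: 9.75% for k=2 and 18.5% for k=4. These are ceilings only, because the four versions share most of their data.

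**3. How closely the two change scores agree**

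Let a be the correlation between weeks -4 and -1, b the correlation of each with week 26, and σ a common SD. All are assumptions, since the SAP gives none.

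- Var(change from B) = 2σ²(1 − b)
- Var(change from P) = σ²[1 + (1 + a)/2 − 2b]
- The covariance of the two change scores equals Var(change from P), so their correlation is the square root of the variance ratio.

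Example with a=0.8, b=0.6: Var(P) = 1 + 0.9 − 1.2 = 0.70 and Var(B) = 2 × 0.4 = 0.80, in units of σ². The ratio is 0.875 and the correlation √0.875 = 0.935.

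| a, b | Variance ratio P/B | Correlation | P or B significant under no effect (large-sample bivariate normal, limits ±1.96) |
|---|---|---|---|
| a = b (0.5, 0.7 or 0.8) | 0.750 | 0.866 | 7.3% |
| 0.7, 0.5 | 0.850 | 0.922 | 6.8% |
| 0.8, 0.6 | 0.875 | 0.935 | 6.7% |

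Change from P therefore has 25% less variance than change from B only if all visits correlate equally, and 12.5% less in the last row.

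**4. Simulation under no effect**

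Assumed: SD 12 mmHg; 10, 20 or 40 per arm (40 is half of the target of 80 in 1.2, which was not reached); the five correlation pairs above; 40,000 trials per setting (Monte Carlo SE about 0.13 points). The section 2.4 rule was applied as written: a covariate enters only if its own baseline comparison has p<0.05. The model was fitted as an ordinary linear model, because the SAP specifies no random effects.

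| Quantity | At least one p<0.05 |
|---|---|
| Each t-test alone | 4.7-5.2% |
| Each section 2.4 model alone | 4.0-4.9% |
| P or B t-test | 6.3-7.5% |
| Any of four, baseline BP the only candidate covariate | 6.8-7.7% |
| Any of four, five further candidates (each adding SD 2.4 mmHg to week 26) | 7.0-8.3% |

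A separate simulation with totals of 40 and 80 and other correlations gave 7.2-8.3% for any of four.

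**5. Simulation with an assumed 6 mmHg effect**

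The P and B t-tests disagree on whether p<0.05 in about 5-20% of trials (9-20% in 14 of the 15 settings). The exception, near 5%, is 40 per arm with all correlations 0.8, where both tests are nearly always significant. Not all four versions agree in 5.5-21.0%.

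**6. Where the spread comes from**

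On the same baseline (P), with baseline BP the only candidate covariate, the t-test and the section 2.4 model disagree in only 0.2-0.8% of trials under no effect and 0.2-1.6% with the 6 mmHg effect. Most of the numerical spread comes from P versus B.

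**The case against.** The strongest reply is that this is a feasibility study stopped early, and that 2.4 declares the analysis exploratory. Both baselines are listed openly, so nothing is hidden, and reporting every version in full would remove most of the harm. The e.g. in 2.9.4.1 suggests that the t-test is an illustration. The two methods seldom disagree (step 6), and inflation arises only if any one version may be taken as the primary result, which no section says.

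Much of this is true, and it limits the size of the point. P and B together are a missing ranking, not a contradiction, and the inflated rates are conditional on an either-will-do reading. The wording of H0 and H1 is loose but can be understood from the sentence before them.

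It does not remove the conflict. Section 2.4 reserves a 5% level for the primary endpoint in contrast to the exploratory secondary endpoints, and 2.9.4.1 calls 0.05 the level of the trial, so the primary p-value is treated as special without being identified. If the t-test is only an example, then the section that should fix the primary test fixes none, while 2.9.1 still says unadjusted with no such qualifier. The SAP does not exclude the either-will-do reading.

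If baseline BP were always in the model, the any-of-four rate would be 8.0-9.7%. That is not the rule in 2.4, so the conclusion does not rely on it.

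**Conclusion.** The concern holds, and should be corrected before the results are read. The SAP contradicts itself on the primary method, leaves two baselines unranked, and attaches a 5% level to an analysis it also calls exploratory only. This follows from the text and needs no simulation.

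Under the assumed inputs, each single version stays close to or slightly below 5%, and an unrestricted choice among the four gives 6.8-8.3%. With an assumed 6 mmHg effect, the choice of baseline alone changes the significance call in about 5-20% of trials. That is a difference in whether p falls below 0.05, not a reversed effect. The SD, correlations, covariates, arm sizes and effect are all assumptions, and the SAP does not state the final number randomised.

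**What to change.** Before unblinding, name one primary analysis in identical terms in 1.1.1, 2.1, 2.4 and 2.9.4.1:

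- **Endpoint and model:** for example, change in 24-h systolic ambulatory BP at week 26 from P (or from B, if the sponsor prefers), by a linear model with that baseline value as covariate. Report the adjusted difference with its 95% CI.
- **Covariates:** fix any others, and any random effects, in advance. Delete the rule that picks covariates by baseline significance, because it leaves the model unknown until the groups have been compared.
- **Section 2.9.4.1:** remove the unpaired t-test as primary test and write H0 and H1 for the mean change.
- **Section 2.9.1:** limit the unadjusted sentence to descriptive or sensitivity use.
- **Sensitivity analyses:** label the other baseline and the t-test as such.
- **Analysis set:** define ITT once, in the same way in 2.3 and 2.4.
- **Status of the 5%:** state either that it applies to this one analysis only, or that the analysis is purely exploratory and no confirmatory claim is made.

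Naming the t-test as primary would also end the contradiction, but a baseline-adjusted model with fixed covariates is the better choice. The cost is SAP wording: no new data or visits, and every other version can still be reported. The SAP does not show whether unblinding has already taken place. If it has, the choice and its timing should be disclosed in the report.
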